In addition to the primary study objective, investigate the following questions: 1) can measurements made by the CoVa™ 2 (particularly stroke volume (SV), cardiac output (CO), fluid status, arrhythmia detection, and basic vital signs) be successfully made before, during, and after an EP procedure?; 2) is there correlation between CoVa™ 2-measured parameters (particularly volume status, heart rate and arrhythmia, SV, and CO) before, during, and after an EP procedure?; 3) does RF ablation during an EP procedure interfere with CoVa™ 2 measurements?; 4) does a 200-300 Joule shock during a DC cardioversion procedure interfere with CoVa™ 2 measurements?; and 5) is the CoVa™ 2's usability suitable for hospital clinicians?

Description of Study Design

Study subjects scheduled for an EP procedure who have signed an informed consent form (ICF) will be admitted to the study. Prior to the EP procedure (e.g. in a hospital room or operating room at NYU Medical Center), an employee of NYU will prep the subject's skin with an alcohol wipe, apply the CoVa™ 2 Sensor using a pair of disposable electrodes, connect it to the Gateway Device using Bluetooth®, and ensure that it is transmitting information from the CoVa™ 2 Sensor through the Gateway Device to the Cloud-based System. All transmitted information will be de-identified. All subjects will continue to be monitored with standard of care equipment.

Once this data pathway is verified, measurements will be made from the subject for a period of approximately 2 hours prior to the EP procedure. More specifically, measurements will be made continuously for a period of about 90 seconds, and then, as described above, information will be transferred from the CoVa™ 2 to the Gateway Device, and from the Gateway Device to the Cloud-based System. This process will take roughly 120 seconds. Once it is complete, this 'duty cycle' will be repeated for the duration of the 2-hour period, i.e. measurements will again commence for a period of about 90 seconds, and then paused for about 120 seconds while data is wirelessly transmitted as described above.

Measurements will be temporarily halted as the subject is moved into the operating room and prepped for the EP procedure. Prior to the procedure, the CoVa™ 2 sensor will be attached to an external power supply as described above. Once the procedure is started, measurements will be made in the same manner as described above.

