The primary endpoint will be if at least 50% of subjects studied in this trial are able to be discharged relatively early from the hospital if they are monitored with CoVa™ 2, as determined through a retrospective analysis. A detailed retrospective statistical report will be the determining factor in meeting this success criteria.

Study Enrollment and Withdrawal

Inclusion Criteria

In order to be eligible to participate in this study, an individual must meet all of the following criteria:

1. Patients with arrhythmias and other cardiac conditions that are scheduled for EP procedures.
2. Subject is over 22 years of age at the time of consenting
3. Subject and/or legally authorized representative is willing to undergo the informed consent process prior to enrollment in the study

Exclusion Criteria

An individual who meets any of the following criteria will be excluded from participation in this study:

1. Pregnant subjects
2. Subjects who are participating in another clinical study that may affect the results of either study

3. Subjects who are unwilling or unable to wear the sensor (and electrodes) for a period of up to 14 hours
4. Subjects who are considered by the principle investigator to be medically unsuitable for study participation

Vulnerable Subjects

Vulnerable subjects will not be utilized in this study. In the case of a vulnerable population patient being identified; they will not be included in the study or analysis..

Strategies for Recruitment and Retention

No NYULMC media will be used to recruit subjects. Subjects that are scheduled for an EP procedure and meet the inclusion criteria will be approached for enrollment.

Subjects will be consented in a quiet and private environment. Subjects will be given the opportunity to take the written consent form home to review overnight.

Use of DataCore/Epic Information for Recruitment Purposes

This study will utilize EPIC to identify subjects. Once potential subjects have been identified, the study team will notify the treating physician (TP) that they have patients eligible to participate. The study team will obtain approval from the treating physician to approach the eligible patient for the study.

Duration of Study Participation

The total duration of study participation is about 1.5 days. This includes:

Written Informed Consent Process: 1 day

Study Procedure: 1 day

Measurement prior to EP Procedure: 1-3 hours

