The PI will confirm prior to enrollment that each subject qualifies for the study. The eligible subject will be approached by the research team. All patients willing to participate will personally sign and date the latest IRB approved version of the consent form. Written and verbal versions of the participant information and informed consent will be presented to the participants detailing no less than: the exact nature of the study; the implications and constraints of the protocol; the known side effects and any risks involved in taking part. It will be clearly stated that the participant is free to withdraw from the study at any time for any reason without prejudice to future care, and with no obligation to give the reason for withdrawal. The participant will be allowed as much time as wished to consider the information, and the opportunity to question the Investigator, their general practitioner or other independent parties to decide whether they will participate in the study. Written Informed Consent will then be obtained by means of participant dated signature and dated signature of the person who presented and obtained the informed consent. A copy of the signed Informed Consent will be given to the participants. The original signed form will be retained at the study site, in a research binder maintained by the study team in a locked cabinet. All documents will be stored safely in confidential conditions. On all physical and electronic study-specific documents, other than the signed consent, the participant will be referred to by a study participant number/code, not by name.

Visit 2 (Day of EP procedure)

- Ensure the subject has no additional questions regarding the study
- Once the subject has been prepped for surgery, apply the sensor to the subject's upper chest using the toSense approved electrodes
- Connect the device to the power source
- Study participant will be assigned a study number/code

- All data transmitted by the CoVa2 device will be de-identified.
- Run several test measurements on the sensor to ensure that the device is actively measuring on the subject
- Explain to the subject that the sensor will measure for a 90 seconds period, with 120 second pause in between measurements
- Measurements will not be made while the subject is transferred to and from the surgery room
- Measurements will be made until the patient is discharged

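### The Visit 2 list first applies the sensor after surgical prep and has no pre-procedure recording step, while the design section records about 2 hours before prep, so the baseline readings are at risk

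*Protocol*

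**What the plan says.** Three places in the protocol bear on when the pre-procedure readings are taken.

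- **Description of Study Design.** The sensor is applied and the data pathway verified. Then "measurements will be made from the subject for a period of approximately 2 hours prior to the EP procedure". After that, "Measurements will be temporarily halted as the subject is moved into the operating room and prepped for the EP procedure". External power is attached before the procedure, and measuring resumes once the procedure has started. First application may take place in either of two settings: "Prior to the EP procedure (e.g. in a hospital room or operating room at NYU Medical Center".
- **Duration of Study Participation.** "Measurement prior to EP Procedure: 1-3 hours".
- **Study Procedures and Schedule, Visit 2 (Day of EP procedure).** "Once the subject has been prepped for surgery, apply the sensor". The next equipment step is "Connect the device to the power source". The list then calls for several test measurements, an explanation of the 90 s on, 120 s off cycle to the subject, no measuring during transfer in either direction, and measuring until discharge. It gives no earlier application step and no pre-procedure recording period.

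The primary objective, secondary objectives 1 and 2, and the Statistical Analysis entry of the Protocol Summary all refer to measurements before, during and after the procedure.

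**The concern.** The design section puts prep after the baseline recording. The Visit 2 list puts first application of the sensor after prep. If prep is the same step in both places, the baseline window has closed by the time the sensor goes on.

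The study has one arm and no control group, so each subject's own earlier readings are the only pre-procedure reference. Readings not taken on the day cannot be recovered, and no later analysis can restore them. If some staff follow the design section and others the Visit 2 list, the baselines of about 20 subjects would come from different states: some from a subject waiting before prep, others from a subject already prepped. A change from before to during or after would then partly reflect when the sensor was put on.

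**Working it through.** **1. The two orders side by side**

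| Step | Description of Study Design | Visit 2 list |
|---|---|---|
| 1 | Apply sensor, verify data pathway | Prep for surgery |
| 2 | Record about 2 hours | Apply sensor |
| 3 | Halt for move and prep | Connect power |
| 4 | Attach external power | Several test measurements |
| 5 | Resume once the procedure starts | Measure until discharge, except during transfers |

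Taken literally, the 2-hour period in the left column ends before prep and application in the right column begins after it. The two do not overlap. In the left column, moreover, recording stays halted from the move until the procedure starts. Any cycles that Visit 2 yields between prep and procedure therefore fall in an interval that the design section does not record at all.

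**2. Size of the planned window**

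Inputs: 90 s measuring and 120 s pause (Description of Study Design, repeated in Visit 2); a window of about 2 hours (Description of Study Design) or 1-3 hours (Duration of Study Participation).

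Cycle length = 90 + 120 = 210 s. Cycles = window / 210 s. Recorded signal = whole cycles × 90 s.

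- 1 hour: 3600 / 210 = 17.1, so 17 cycles, 25.5 min of signal
- 2 hours: 7200 / 210 = 34.3, so 34 cycles, 51 min of signal
- 3 hours: 10800 / 210 = 51.4, so 51 cycles, 76.5 min of signal

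The 1-3 hour range contains the 2-hour figure, so those two statements are compatible. They do not fix one window, however: planned baseline data could differ threefold between subjects.

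**3. What the Visit 2 order leaves**

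Of the pre-prep window: 0 cycles on the literal reading. What remains before the procedure is the test measurements plus any ordinary cycling until the procedure starts. The protocol gives neither the number of test measurements nor the length of that interval, so the amount of post-prep data cannot be calculated.

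**4. Does the power step settle which reading is meant?**

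No. The design section says "Prior to the procedure, the CoVa™ 2 sensor will be attached to an external power supply as described above", which follows the move and prep and so resembles the start of the Visit 2 list. Yet the same sentence points back to an earlier description of the power connection, and no such description precedes it in that section. It can be read either way.

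**The case against.** The best counter-argument is that Visit 2 can be read consistently with the design section. It bars measuring during transfer to the surgery room as well as from it, which has a point only if the sensor is already on before that transfer. Prep is undefined in Visit 2 and could mean preparation on the ward, with operating-room prep following later as the design section describes. The list is also a summary: it has no separate step for recording during or after the procedure either, and it says that measuring continues until discharge. Other sections state the pre-procedure measurement, the study has a single site, and staff are trained on site.

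Much of this stands. It shows that loss of the baseline is not inevitable and that a team reading every section might record it. It does not remove the conflict. The ward-prep reading has to be inferred, and even on that reading Visit 2 gives no recording period before transfer.

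Two stronger inferences are tempting, and the protocol supports neither.

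- A reader might put the loss at 85-91% of baseline cycles, from 3-5 test cycles in place of 34: (34 − 5)/34 = 85% and (34 − 3)/34 = 91%. The 3-5 is an assumption, and nothing says that recording stops after the tests.
- A reader might infer that the primary endpoint is compromised. That endpoint is whether at least 50% of subjects could be discharged relatively early, and it is not defined as a change from baseline.

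**Conclusion.** The concern holds as a conflict between the day-of-procedure list and the design section over when the sensor goes on relative to prep, together with the absence of a pre-procedure recording step from that list. At stake per subject is a planned window of about 34 cycles (17 to 51 over 1-3 hours), none of which would be recorded on the literal Visit 2 order. That figure assumes that prep means the same step in both sections and that the stated duty cycle runs without interruption. How many subjects would be affected, and how much post-prep data would remain, cannot be derived from the protocol.

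The consequence is a risk of missing or mixed baselines in the before/during/after comparison that the primary objective and secondary objectives 1 and 2 call for. It should be settled before enrolment because the readings cannot be obtained afterwards.

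**What to change.** - Reconcile Description of Study Design, Duration of Study Participation and Visit 2 so that the Visit 2 list carries one order: sensor application, pre-procedure recording, halt for transfer and prep, restart.
- State one pre-procedure window in all three places, and say what prep refers to.
- Record for each subject the time of sensor application and the time prep starts.
- Identify baseline readings by those times. Report any cycles taken after prep but before the procedure separately from the pre-prep baseline. They need not be discarded; the protocol gives no ground for a flat ban on them.

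The cost is a wording amendment, with the IRB review that any amendment needs, and two time stamps per subject. Some subjects may turn out to have no pre-prep baseline, which would reduce the number contributing to that comparison.
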